4.6.2 Stool Consistency and Ease of Passage Analysis Conventions

Only stool consistency and ease of passage scores associated with SBMs will be used in analyses (i.e., excluding BMs where it was indicated that rescue medication had been used within 24 hours).

4.6.3 Analysis of the Primary Efficacy Endpoint

The primary efficacy endpoint is the change from baseline in weekly CSBM rate during the Fixed Dose period. The primary analysis will be based on the Fixed Dose Population. The primary efficacy analysis will be performed via an analysis of covariance (ANCOVA) model with change from baseline in weekly CSBM rate as the dependent variable, treatment (ENT-01 or placebo) as the independent variable, and baseline weekly CSBM rate as a covariate.

As a supplemental analysis, the treatment effect for the primary efficacy endpoint will be summarized by the weekly CSBM rate subgroups (0 – 0.9, 1.0 – 3.0). The analysis will be performed for both Efficacy Evaluable population and Fixed Dose population.

The study will be considered a success if the p-value for the comparison of treatment groups from the ANCOVA model using the Fixed Dose population is significant (p<0.05).

Change from baseline in weekly CSBM rate will also be summarized by the specific fixed dose for patients. These summaries will be descriptive in nature only and no inferential statistics will be performed.

A linear trend test for weekly CSBM rate within each treatment group across baseline, fixed dose, and single blind periods will be conducted by using mixed model repeated measures (MMRM) methods, where the Baseline, Fixed Dose, and Single Blind periods are assigned values of 0,1, and 2 respectively for modeling purposes. Baseline CSBM rate (0-0.9/1.0-3.0) is included as a factor, with subject intercept and slope as random effects in the mixed model. The trend test will also be conducted across all subjects, including both Placebo and ENT-01 treatment groups in the model as a factor (fixed effect).

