	
and conditional power calculations are based on the results of the initial cohort of subjects in this Phase 2b study.

	
Analysis Populations
 
 • Safety Population: The Safety Population will consist of all subjects who receive at least one dose of study medication during the study. • Modified ITT Population: The modified Intent-to-Treat (mITT) Population will include subjects who are randomized and have the stool diary assessments both at baseline and at least one post baseline time-point. • Fixed Dose Population: The Fixed Dose Population will include all subjects who are in mITT Population who enter the Fixed Dose period of the study. • Efficacy Evaluable Population: The Efficacy Evaluable Population will include subjects who are in the Fixed Dose Population, complete the Fixed Dose period, are compliant with study medication in the Fixed Dose period and have no major protocol deviations. 
Analysis Methods
 
Descriptive summary statistics will be presented for the safety and tolerability endpoints by treatment group and overall. Continuous variables will be summarized using the number of observations, mean, standard deviation, median, minimum, and maximum. Categorical variables will be summarized using frequency counts and percentages.
 
The primary efficacy endpoint is the change from baseline in weekly CSBM rate during the Fixed Dose period. The primary analysis will be based on the Efficacy Evaluable Population. The primary efficacy analysis will be performed via an analysis of covariance (ANCOVA) model with change from baseline in weekly CSBM rate as the dependent variable, treatment (active or placebo) as a factor, and a subject's baseline weekly CSBM rate as a covariate. The comparison of the active versus the placebo treatment group will be at the two-sided 0.05 significance level.
 
Interim Analysis
 
An unblinded interim analysis was performed after the initial cohort of the study. A blinded second interim analysis may be performed after the 40th subject (in the 1:1 randomized cohort) completes the Fixed Dose period (i.e. Visit 4).

Initial Date	December 2018
Completion Date	November 2021

Table 1. Study Schedule of Events

	Visit 1 Screening	Visit 2 Randomization	Visit 3 Follow-Up	Visit 4 End of Treatment	Visit 5 End of Placebo	Visit 6 End of Study	Early Termination
	Day -21	Day 1 (+/- 8 days)	Day 11 (+/- 3 day)	Day 26 (- 2 days)	Day 39 (+/- 8 days)	Day 69 (+/- 8 days)	

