9.2.4 Efficacy Analyses

9.2.4.1 Primary Efficacy Endpoint Analyses

The primary efficacy endpoint is the change from baseline in weekly CSBM rate during the Fixed Dose period. The primary analysis will be based on the Efficacy Evaluable Population. The primary efficacy analysis will be performed via an analysis of covariance (ANCOVA) model with change from baseline in weekly CSBM rate as the dependent variable, treatment (active or placebo) as a factor, and a subject's baseline weekly CSBM rate as a covariate. The comparison of active versus placebo treatment group will be tested at the two-sided 0.05 significance level. Summary statistics will also be presented.

As a supplemental analysis, the treatment effect for the primary efficacy endpoint will be summarized by the weekly CSBM rate subgroups (0-0.9, 1.0 – 3.0). The primary efficacy analysis will also be performed on the mITT and Fixed Dose Populations.

As an additional supplemental analysis, the change from baseline in weekly CSBM rate using the subject's last 2 weeks of the Treatment Period will be analyzed using the ANCOVA model described for the primary endpoint using the mITT population.

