3. SUBJECT POPULATIONS

3.1. Population Definitions

The following subject populations will be evaluated and used for presentation and analysis of the data:

- **Safety Population:** The Safety Population will consist of all subjects who receive at least one dose of study medication during the study. Subjects will be analyzed based on the treatment that they actually received. All safety analyses will be based on this population.
- **Modified ITT Population:** The modified Intent-to-Treat (mITT) Population will include subjects who are randomized and have the stool diary assessments both at baseline and at least one post baseline time-point. Subjects who are found later to have inclusion/exclusion violations will be excluded from the mITT population.
- **Fixed Dose Population:** The Fixed Dose Population will include all subjects who are in mITT Population who enter the Fixed Dose period of the study and are in the treatment period for at least seven days, not including the date of randomization.
- **Efficacy Evaluable Population:** The Efficacy Evaluable Population will include subjects who are in the Fixed Dose Population, complete the Fixed Dose period, are compliant with study medication in the Fixed Dose period, and have no major protocol deviations.
- **Pharmacokinetics Population:** Pharmacokinetics Population will include subjects with a least one L-Dopa PK result.

The precise reasons for excluding subjects from the Efficacy Evaluable Population will be fully defined and documented prior to the unblinded interim analysis.

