3.2. Protocol Violations

At the discretion of the sponsor, major protocol violations as determined by a review of the data prior to the database locks or unblinded interim analysis and the conduct of statistical analyses may result in the removal of a subject's data from the Efficacy Evaluable Population. The sponsor, or designee, will be responsible for producing the final protocol violation file (formatted as a Microsoft Excel file), in collaboration with Cytel and the data monitoring group as applicable; this file will include a description of the protocol violation, and clearly identify whether or not this violation warrants exclusion from the Efficacy Evaluable Population. This file will be finalized prior to the database locks.

All protocol violations will be presented in the data listings.

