5. CHANGES TO PLANNED ANALYSES

As of this date, there have been no changes between the protocol-defined statistical analyses and those presented in this statistical plan.

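### The protocol and the SAP name different primary populations, the only success criterion sits on the SAP's choice, and the protocol's last-2-weeks mITT ANCOVA is missing from the SAP

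*SAP*

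**What the plan says.** **Primary population.** The protocol synopsis says "The primary analysis will be based on the Efficacy Evaluable Population", and Protocol 9.2.4.1 repeats it, with mITT and Fixed Dose as supportive sets. SAP 4.6.3 says "The primary analysis will be based on the Fixed Dose Population". SAP 4.6 agrees and makes mITT and Efficacy Evaluable supportive.

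**Success criterion.** Only the SAP states one: the trial succeeds if the p-value "from the ANCOVA model using the Fixed Dose population is significant" at 0.05. The protocol gives a two-sided 0.05 test in the Efficacy Evaluable set and no separate success rule.

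**Definitions.** In both documents Efficacy Evaluable is the Fixed Dose set restricted to subjects who complete the Fixed Dose period, are compliant in it and have no major deviations. The SAP narrows two sets beyond Protocol 9.0. Its Fixed Dose set takes mITT subjects "who enter the Fixed Dose period of the study and are in the treatment period for at least seven days", and for mITT it adds: "Subjects who are found later to have inclusion/exclusion violations will be excluded from the mITT population".

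**Exclusions.** SAP 3.2 allows removal from Efficacy Evaluable on these terms: "At the discretion of the sponsor, major protocol violations as determined by a review of the data prior to the database locks". The violation file must be final before database lock, and SAP 3.1 requires the exclusion reasons to be documented before the unblinded interim analysis.

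**Supplemental analysis.** Protocol 9.2.4.1 adds that change in weekly CSBM rate over the subject's last 2 weeks of treatment "will be analyzed using the ANCOVA model described for the primary endpoint using the mITT population". The SAP has no such analysis. SAP section 5 nevertheless states, as of its date, that "there have been no changes between the protocol-defined statistical analyses and those presented in this statistical plan".

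**The concern.** Two documents that both claim to define the primary test point to different sets of subjects. If the two results fall on opposite sides of 0.05, nothing in the text says which decides the trial. The question is more exposed here because cohort 1 has already been unblinded (Protocol 9.2.6) and SAP 4.2 makes no multiplicity adjustment.

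Both candidate sets are selected on events after randomisation, and Efficacy Evaluable more heavily. The protocol's last-2-weeks mITT ANCOVA is the one analysis of weekly CSBM rate on treatment that does not depend on when, or whether, a dose became fixed. The SAP's mITT repeat does not replace it: under SAP 2.5 a subject with fewer than seven treatment days has no Fixed Dose period, and so no Fixed Dose value.

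**Working it through.** **1. Text comparison.**

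| Item | Protocol | SAP |
|---|---|---|
| Primary set | Efficacy Evaluable | Fixed Dose |
| Supportive sets | mITT, Fixed Dose | mITT, Efficacy Evaluable |
| Success rule | none beyond the 0.05 test | p<0.05 in Fixed Dose |
| Seven-day condition for Fixed Dose | no | yes |
| Later-found eligibility violators in mITT | not removed | removed |
| Last-2-weeks mITT ANCOVA | yes | absent |
| Declared changes | not applicable | none |

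**2. The plan's own figure.** SAP 4.1, first part: 64 evaluable at 3:1 (48/16), difference 2.4 − 0.5 = 1.9, SD 2.0. SE = 2.0 × √(1/48 + 1/16) = 0.577; noncentrality 1.9/0.577 = 3.29 on 62 df; power 89.96%. The stated 90% reproduces. The part 2 conditional powers cannot be checked, because cohort 1's test statistic and the combination rule are not given; nothing below relies on them.

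**3. How often the two verdicts would differ.** Inputs:
- Randomised: 54 + 40 = 94 ENT-01 and 18 + 40 = 58 placebo.
- SD 3.88 and difference 3.55 − 1.28 = 2.27 (Protocol 9.2.5). A smaller difference, 1.5, is assumed.
- Efficacy Evaluable: 64/72 = 89% in both cohorts (48 + 36 = 84 and 16 + 36 = 52), or 89% in cohort 1 and 60/80 = 75% in cohort 2 (48 + 30 = 78 and 16 + 30 = 46). SAP 4.1 calls these subjects evaluable; Protocol 4 describes the same 60 of 80 as completing all visits.
- Fixed Dose retention is not in the documents: assumed 95% (89/55), range 90% (85/52) to 100% (94/58).

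Efficacy Evaluable is drawn as a random subset of Fixed Dose, so there is no bias by construction. A two-sample t-test stands in for the ANCOVA, with 2,000,000 simulated trials per row.

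| Fixed Dose n | Efficacy Evaluable n | Verdicts differ at 2.27 | Verdicts differ at 1.5 | At least one p<0.05 under the null |
|---|---|---|---|---|
| 89/55 (95%) | 84/52 | 3.2% | 7.6% | 6.1% |
| 89/55 (95%) | 78/46 | 6.6% | 13.6% | 6.8% |
| 94/58 (100%) | 84/52 | 4.4% | 10.9% | 6.5% |
| 94/58 (100%) | 78/46 | 7.7% | 16.0% | 7.1% |
| 85/52 (90%) | 84/52 | 0.9% | 2.1% | 5.4% |
| 85/52 (90%) | 78/46 | 5.4% | 11.0% | 6.5% |

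Check on the last column: nested tests have correlation √f, where f is the ratio of n₁n₂/(n₁+n₂). For 84/52 in 89/55, f = 32.1/34.0 = 0.945; for 78/46, f = 28.9/34.0 = 0.85. The bivariate normal gives 6.0% at f = 0.95 and 6.8% at f = 0.85, in agreement.

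**4. Cohort 1 held fixed.** Cohort 1 has been observed, so hold it at 2.27, SD 3.88, in both sets (assumed) and draw only cohort 2. At 95% retention (51/17 plus 38/38, against 48/16 plus 36/36 or 30/30) the verdicts differ in 1.7% or 4.1% of trials at 2.27, and in 4.2% or 8.8% at 1.5.

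**5. Why the last-2-weeks analysis needs a short-exposure rule.** Protocol 9.2.4.1 gives none for fewer than 14 treatment days. With the SAP 4.6.1 formula, 7 × CSBMs / days, a single CSBM gives 7.0 per week over 1 day, 2.33 over 3 days and 1.17 over 6 days.

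**The case against.** The best defence is that nothing is hidden. Each document analyses the primary endpoint in all three populations, and the exclusion reasons and violation file must be settled before unblinding or lock. A reader might infer that the sponsor could choose exclusions after seeing results; SAP 3.1 and 3.2 do not support that. These safeguards fix who is in each set, but not which set is confirmatory.

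A reader might also infer that the population was switched because of cohort 1's results. The documents do not show this. The SAP keeps a Day −14 screening visit, narrower visit windows and sleep endpoints that differ from protocol version 7.0, so it may follow an earlier version. That would explain the mismatch without resolving it.

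Two further readings go too far. First, early withdrawals are not wholly undefined. SAP 2.5 covers a subject on one dose until withdrawal after at least seven days, and it extends short fixed-dose periods back to seven days. Only the subject who changed dose and withdrew while still escalating is unclear. Second, subjects with under seven treatment days are not dropped from everything. They remain in safety and disposition summaries, may contribute washout data, and could enter the SAP 4.6.3 trend model through their baseline if it is run in mITT. What they lack is a Fixed Dose value.

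On size, SAP 4.1 also gives unequal SDs (4.11 and 2.38). At 89/55 the SE is then √(4.11²/89 + 2.38²/55) = 0.54, against 3.88 × √(1/89 + 1/55) = 0.67, so disagreement at 2.27 would be rarer than in the table. That objection to the size stands.

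**Conclusion.** The conflict is real in current body text and must be fixed: the two documents designate different confirmatory tests, and SAP section 5 denies any difference. The missing last-2-weeks mITT ANCOVA is a lesser matter, a gap in supportive analysis.

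The size is modest. With random exclusions, SD 3.88, pooled cohorts and 95% Fixed Dose retention, the verdicts differ in about 3% to 7% of trials at 2.27 (1% to 8% over 90% to 100% retention) and in about 8% to 14% at an assumed 1.5 (2% to 16%). With cohort 1 held at 2.27, the 95% figures are about 2% to 4% and 4% to 9%. If either test could be called primary, the null chance of a significant result is about 6% to 7% (5.4% to 7.1% over the range). That covers only the choice between the two tests, not the earlier interim look.

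A reader might infer that one set inflates the effect. The documents give no early-stop rate by arm or by day, so neither the size nor the direction of any selection bias can be computed.

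**What to change.** Before cohort 2 is unblinded:

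1. Name one primary population, with one definition, and one success criterion, identically in the protocol and the SAP. Of the two existing sets, Fixed Dose removes fewer subjects for post-randomisation events, since Efficacy Evaluable is a subset of it. Report the other sets as sensitivity analyses.
2. State whether a subject who changed dose and withdrew while still escalating, after seven or more days, has entered the Fixed Dose period.
3. Restore the last-2-weeks mITT ANCOVA in SAP 4.6.3 on the Protocol 9.0 mITT definition, with a stated rule for subjects with fewer than 14 treatment days, or record why it was dropped.
4. Correct SAP section 5 to list these differences.

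Separately, the passages on reaching a DLT before a prokinetic effect need to be reconciled. Protocol 3.1 (safety) and SAP 2.3 list it as an individual stopping criterion, and Protocol 8.15 omits it. Protocol 3.1 (efficacy) lets the Fixed Dose period start at the highest dose without a DLT, and SAP 2.6.6 continues such subjects at that dose. No clinical rule is proposed here.

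The cost is wording in two documents and at most one supportive analysis on diary data already collected. The supportive estimate may come out smaller than the primary one.

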Objectives	
Primary Objectives:
 
To evaluate the safety, tolerability, and efficacy of repeated oral doses of ENT-01 for up to 25 days in subjects with Parkinson's Disease- related constipation in a randomized, double-blind, placebo-controlled study.
 
 • Primary Safety Objective: The primary safety objective of this study will be evaluation of the safety of repeated daily oral doses of ENT-01 for up to 25 days in subjects with PD-related constipation. • Primary Tolerability Objective: The primary tolerability objective will be evaluation of recurrent vomiting, recurrent diarrhea, abdominal pain and dizziness. • Primary Efficacy Objective: The primary efficacy objective will be evaluation of the efficacy of repeated daily oral doses of ENT-01 for up to 25 days in improving CSBM rate. 
Secondary Objectives:
 
 • To determine if the correct starting dose (75 mg or 150 mg) can be predicted from the baseline weekly CSBM rate. • To collect information on the effect of ENT-01 on CSBM, SBM, ease of passage, consistency, suppository/enema use and subjective bowel function and quality of life (QOL). 
Exploratory Objectives:
 
 • To determine any change in efficacy in the blinded placebo withdrawal and washout periods. • To collect information on the effect of ENT-01 on motor and non-motor symptoms of Parkinson's disease including mood, memory, and hallucinations/delusions. • To collect information on the effect of ENT-01 on levodopa absorption. • To collect information on the effect of ENT-01 on the stool microbiome
Number of Subjects	The study will have approximately 152 randomized subjects, with up to approximately 80 subjects being randomized in this extension and captured in this amendment.
Study Description	Multicenter, randomized, double-blind, placebo-controlled, study of daily oral doses of ENT-01 for up to 25 days
Study Population	Parkinson's Disease with constipation
Study Drug Administration	Oral
Inclusion/Exclusion Criteria	The study population is defined as subjects who meet the following criteria: Inclusion Criteria:

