4 STUDY DESCRIPTION

The first part of this Phase 2b study was conducted as a multicenter, randomized, double-blind, placebo-controlled study. Each subject's total study duration was no more than 10 weeks and total active dosing days were 25 days. 72 subjects were randomized in a 3:1 ratio to active treatment or placebo, respectively. 54 subjects received active treatment and 18 received placebo. Randomization was stratified on baseline weekly CSBM rate. Subjects with baseline CSBM rates of 1.0-3.0/week were randomized to begin with 75 mg of ENT-01 (3 tablets) or 3 placebo tablets: subjects with baseline CSBM rates of 0-0.9/week were randomized to begin with 150 mg of ENT-01 (6 tablets) or 6 placebo tablets. The dose was then escalated every 3 days in increments of 25 mg (or 1 placebo tablet) until either an effective dose, a maximum tolerated dose or 250 mg was reached, whichever came first. The dose was then "fixed" at that dose for the remainder of the 25-day treatment period.

In this amendment of the protocol, the study will be conducted as a multicenter, randomized double-blind, placebo-controlled study. Each subject's total study duration will be no more than 10 weeks and total active dosing days will be 25 days. Up to 80 subjects will be randomized across up to 25 U.S. sites to ensure approximately 60 subjects will complete all visits, assuming a 25% early termination rate. Randomization will be 1:1 to active treatment or placebo.

Randomization will be stratified based on baseline weekly CSBM rate. Subjects with baseline CSBM rates of 1.0-3.0/week will be randomized to begin with 75 mg of ENT-01 (3 tablets) or 3 placebo tablets: subjects with baseline CSBM rates of 0-0.9/week will be randomized to begin with 150 mg of ENT-01 (6 tablets) or 6 placebo tablets. The dose will then be escalated every 3 days in increments of 25 mg (or 1 placebo tablet) until either an effective dose, a maximum tolerated dose or 250 mg is reached, whichever comes first. The dose will then be “fixed” at that dose for the remainder of the 25-day treatment period. The dosing logic is illustrated in the diagram below.

- The subject will be randomized to either placebo or ENT-01, with the starting number of tablets based on the baseline CSBM rate.
- The dose will be escalated every 3 days by 1 tablet (25mg ENT-01 or placebo)
- If the subject passes at least 1 CSBM/day on each of 3 consecutive days the dose is “fixed.” Otherwise, the dose is escalated.

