2. STUDY DESIGN

2.1. Synopsis of Study Design

This study will be conducted as a multicenter, randomized, double-blind, placebo-controlled study in patients with Parkinson's Disease and constipation.

This study has two parts. The first part of this randomized approximately 72 subjects in a 3:1 to treatment or placebo ratio (double-blind), with approximately 54 subjects allocated to the treatment groups and approximately 18 to placebo. In the second part of the study, an additional 80 patients (approximately) will be randomized 1:1 to treatment or placebo (double-blind) with approximately 40 subjects allocated to each group.

In both parts of the study, the study was conducted as a multicenter, randomized, double-blind, placebo-controlled study. A subject's total study duration was no more than 10 weeks and total active dosing days was a maximum of 25 days.

During the active dosing period, patients will be able to increase/adjust their dose every three days. This is called the Dose Adjustment period. After the subject documents two complete spontaneous bowel movements in three days, the subject will fix at the dose for the remainder of the study. This is called the Fixed Dose period. After completing up to 25 days of dosing, all subjects will be given placebo for 2 weeks (single-blind) followed by 4 weeks of wash-out.

Figure 1. Visit Schedule Overview					
Visit 1	Visit 2	Visit 3	Visit 4	Visit 5	Visit 6
Screening	Randomization and Drug Dispensation	Follow up	Single Blind Placebo Withdrawal	Wash Out	End of Study
Day -14	Day 1	Day 11 +/- 1 day	Day 25 - 3 days	Day 39 +/- 2 days	Day 69 +/- 3 days

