4.2. General Statistical Methods and Data Handling

General Methods

All outputs will be incorporated into Microsoft Excel or Word files, sorted and labeled according to the International Conference on Harmonisation (ICH) recommendations, and formatted to the appropriate page size(s).

Tabulations will be produced for appropriate demographic, baseline, efficacy, pharmacokinetic and safety parameters. For categorical variables, summary tabulations of the frequency and percentage within each category (with a category for missing data) of the parameter will be presented. For continuous variables, the mean, median, SD, minimum and maximum values will be presented. Time to event data will be summarized using Kaplan-Meier Methodology using 25th, 50th (median), and 75th percentiles with associated 2-sided 95% confidence intervals, as well as percent of observed event rate and summary statistics for the follow-up time.

Formal statistical hypothesis testing will be performed on the efficacy endpoints with all tests conducted at the 2-sided 0.05 level of significance. Summary statistics will be presented, as well as confidence intervals on selected parameters, as described in the sections below.

For all analyses, baseline will be defined as the most recent measurement prior to the date and time of the administration of ENT-01 or placebo. Therefore, baseline may be on the same day as the dose of study treatment, but prior to the administration of the study treatment.

Computing Environment

All descriptive statistical analyses will be performed using SAS statistical software (Version 9.4), unless otherwise noted. Medical History and Adverse Events will be coding using the latest MedDRA version available upon the study start. Concomitant medications will be coded using the latest World Health Organization (WHO) Drug version available upon the study start.

Methods of Pooling Data

Not applicable to the present study.

Adjustments for Covariates

Statistical analyses for the efficacy endpoints will be adjusted by the randomization strata, the baseline CSBM rate (0 – 0.9 vs. 1.0 – 3.0).

Multiple Comparisons/Multiplicity

Adjustments for multiplicity will not be made for this study.

Subpopulations

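### The primary ANCOVA has no cohort term although part 1 was randomized 3:1 and part 2 is 1:1, so a pooled analysis passes about a quarter of any common cohort difference into the treatment estimate

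*SAP*

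**What the plan says.** SAP 4.6.3 models change from baseline in weekly CSBM rate with "treatment (ENT-01 or placebo) as the independent variable, and baseline weekly CSBM rate as a covariate". Its success rule begins "The study will be considered a success if the p-value for the comparison of treatment groups from the ANCOVA model" and requires p<0.05 in the Fixed Dose Population. Protocol 9.2.4.1 gives the same two terms: "treatment (active or placebo) as a factor, and a subject's baseline weekly CSBM rate as a covariate". SAP 4.2 adds a general statement: "Statistical analyses for the efficacy endpoints will be adjusted by the randomization strata, the baseline CSBM rate". It names no other stratifier.

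On allocation, protocol section 4 reports for part 1 that "54 subjects received active treatment and 18 received placebo". SAP 2.1 says the subjects of part 2 "will be randomized 1:1 to treatment or placebo (double-blind) with approximately 40 subjects allocated to each group".

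On combining the parts, the entry under Methods of Pooling Data in SAP 4.2 is "Not applicable to the present study". Other text treats the trial as one data set:

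- The protocol synopsis states "The study will have approximately 152 randomized subjects".
- Protocol 5.7 analyses subjects overall by assigned treatment.
- SAP 4.2 (Subpopulations) presents results by cohort as an addition.
- Protocol 9.2.5 and SAP 4.1 justify part 2 by conditional power given part 1.

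**The concern.** Allocation depends on cohort, so in a combined data set cohort is associated with treatment by design. If the cohorts also differ in mean change at the same baseline, a model without cohort attributes part of that difference to ENT-01.

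The documents do not give such a difference, but they make one plausible. SAP 4.6.1 says the assessments differ between cohorts. The completeness criterion differs by cohort in all four CSBM definitions. The 24-hour rescue criterion is a self-report answer in cohort 1 and comes from diary dates and times in cohort 2.

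If the difference favours cohort 1, the estimate moves towards ENT-01 and false-positive risk rises. If it favours cohort 2, real drug effect is hidden and power falls. The planned by-cohort results would reveal the difference but would not change the p-value that decides success.

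**Working it through.** **1. The plan's own power figure.** SAP 4.1, part 1: 64 evaluable subjects (48:16 at 3:1), difference 2.4 − 0.5 = 1.9, SD 2.0, two-sided 0.05. The standard error is 2.0 × √(1/48 + 1/16) = 0.577, and 1.9/0.577 = 3.29. Power is 90.8% (normal) or 90.0% (t, 62 df), against 90% stated. It reproduces.

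**2. Does the plan need both parts?** Protocol 9.2.5: difference 3.55 − 1.28 = 2.27, SD 3.88, 10% drop-out. Part 2 alone (36:36) has a standard error of 3.88 × √(2/36) = 0.915 and power of about 70% (69% by t). With the SAP's SDs of 4.11 and 2.38 it is about 81%. The documents state 93% and 90%. Pooling 48:16 with 36:36 gives 91%, and 54:18 with 36:36 gives 92.5%. So part 1 data count in the stated power. The exact combination rule cannot be recovered. With 48:16 in part 1 at the 2.27 effect, a conditional-power calculation for 80 or 60 added subjects gives about 95% and 91% stratified by cohort, or 96% and 93% unstratified, against 93% and 88% stated. The analysed part 1 counts per arm are not given.

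**3. Share of a common cohort difference that enters the estimate.** Let D be cohort 1 minus cohort 2 in change at the same baseline, equal in both arms. Without a cohort term,

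bias = D × (cohort 1 share of ENT-01 − cohort 1 share of placebo).

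- Randomized, 54:18 + 40:40: 54/94 − 18/58 = 0.574 − 0.310 = 0.264
- After 10% drop-out, 48:16 + 36:36: 48/84 − 16/52 = 0.264
- 60 added instead of 80, 54:18 + 30:30: 54/84 − 18/48 = 0.268

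For D = 0.5 and 1 the bias is 0.13 and 0.26 CSBM/week, or 6% and 12% of 2.27. A cohort difference of 0.5 in baseline itself left the share near a quarter (0.25 in simulation).

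**4. Error rates.** These come from a simulated ANCOVA with a baseline covariate, 48:16 + 36:36, with D added to both arms of cohort 1. There were 60,000 null runs and 30,000 power runs per SD case; simulation error on the null runs is about 0.2 points. The values of D are assumptions. D = 2 is an extreme case, larger than the whole planned placebo change of 1.28.

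Two-sided type I error (%):

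| SD (ENT-01 / placebo) | D = 0 | 0.5 | 1 | 2 | Cohort term, any D |
|---|---|---|---|---|---|
| 3.88 both (protocol 9.2.5) | 5.0 | 5.4 | 6.6 | 10.8 | 4.9 |
| 4.11 / 2.38 (SAP 4.1) | 2.8 | 3.2 | 4.4 | 9.1 | 2.9 |
| 2.38 both (assumed null case) | 5.0 | 6.0 | 8.9 | 19.1 | 4.9 |

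Error in ENT-01's favour (nominal 2.5%) at D = 0 / 0.5 / 1 is 2.6 / 3.8 / 5.6%, 1.4 / 2.5 / 4.1% and 2.6 / 4.9 / 8.5% in the three cases.

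Power for a true difference of 2.27 (%):

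| SD (ENT-01 / placebo) | D = 0 | −0.5 | −1 | −2 | Cohort term, any D |
|---|---|---|---|---|---|
| 3.88 both | 90.8 | 87.3 | 82.5 | 69.3 | 88.9 |
| 4.11 / 2.38 | 96.6 | 94.4 | 91.0 | 79.3 | 95.4 |

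With the cohort term, bias was within 0.01 at every D.

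**5. Price of the term.** With cohort in the model the information is 48×16/64 + 36×36/72 = 12 + 18 = 30. The standard error ratio is √[(1/30)/(1/84 + 1/52)] = 1.035. Cohort 1's own treatment effect has weight 48/84 = 0.57 without the term and 12/30 = 0.40 with it.

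**The case against.** No sentence says the success test pools the parts. If only part 2 is tested, or separate part-wise results are combined, the confounding does not arise. That stands: pooling is inferred, although it is the better-supported reading. If part 2 alone is meant, the SAP must say so, and the stated power would not apply.

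D is unknown, and the illustrated range is not small: 0.5 to 1 is 39% to 78% of the planned placebo change of 1.28. Because one definition counts both baseline and Fixed Dose stools within a cohort, some of a wording effect would cancel. If wording shifted the placebo change by 20% (an assumption), D would be about 0.26 and the bias about 0.07, or 3% of 2.27. Type I error would then be close to its D = 0 value. With the SAP's SDs, two-sided error stays below 5% even at D = 1. All this is fair and limits the severity, but the success p-value still depends on an unknown that the model could remove.

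A change in diary question may scale counts rather than shift them. Under a real drug effect that is partly a treatment-by-cohort difference, which a cohort main effect does not remove. This also stands.

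Finally, part 1 has been unblinded, so moving cohort 1's weight from 57% to 40% would follow a look at its result. That is a reason to fix the rule before any further unblinding.

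**Conclusion.** The concern holds and should be fixed. The missing term is a fact of both documents. If the parts are pooled at the planned allocation with similar retention across arms, about 0.26 of any common cohort difference enters the treatment estimate. The actual counts by arm and cohort in the analysis population are not given.

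The consequence depends on D. At D = 0 there is no bias. For an assumed 0.5 to 1 CSBM/week the bias is modest, at 6% to 12% of the planned effect. With the documents' own SDs, two-sided type I error is 3.2% to 6.6%, and power loss for D of the opposite sign is about 2 to 8 points. Larger inflation needs the extreme D or the assumed SD of 2.38 in both arms.

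**What to change.** Add cohort (part 1 at 3:1, part 2 at 1:1) as a fixed factor in the primary ANCOVA in SAP 4.6.3, protocol 9.2.4.1 and the synopsis copy of the model. Carry it into the continuous secondary ANCOVAs of SAP 4.6.4. Under Methods of Pooling Data, replace the present entry with a statement that both parts are combined with adjustment for cohort. If the success test is meant to use part 2 alone, say that instead. Settle this before any further unblinded look.

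The Fisher and log-rank comparisons in SAP 4.6.4 carry the same imbalance if pooled. Stratifying them by cohort would be the parallel change, though the success rule does not depend on them.

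The cost is one model term and the matching text. The standard error rises about 3.5%. If D = 0, power falls from 91% to 89% (SD 3.88) or from 97% to 95% (SDs 4.11 and 2.38). The term does not remove a treatment-by-cohort difference, for which the by-cohort results already planned remain the place to look. It also does not address the extension having been sized after an unblinded interim analysis.
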